In the BRUISE control study AF patients with PM or ICD devices were studied using two different regimens for peri-procedural anticoagulation. Birnie et al reported “clinically significant” device pocket hematomas in 3.5% of on Warfarin and in 16% of patients on heparin bridging therapy.⁽³⁾ In another multi-center study, 9.8% of patients on heparin or Warfarin had significant pocket hematomas after pacemaker implantation.⁽⁴⁾ This is in contrast to the general CIED population, in whom this complication was observed only in 0.2% of implanted individuals in a nationwide experience from Denmark.⁽⁵⁾ Kutinsky et al reported even higher rates of hematoma formation in the presence of clopidogrel and aspirin with continued Warfarin therapy ranging from 9.5 to 24%.⁽⁶⁾ Bleeding complications predispose patients to interruption of OAC therapy, use of reversal agents, infection, and re-operation and prolong hospital stays. Bridging therapy may be associated with increased embolic events due to varying anticoagulation status.⁽³⁾

In contrast, in the MOST study performed in patients with only sick sinus syndrome at entry, bleeding complications with pacemaker implantation were <0.4%.⁽⁷⁾ Dewland et al reported major complication rates with ICD implants in the National Cardiovascular Device registry. They noted device related complications of approximately 1% exclusive of major bleeding and hematomas with ICD implants.⁽⁸⁾

2. Purpose and Rationale

The rationale of this study is based on the long half-life of Edoxaban and its potential for reduced bleeding risk in comparison to Warfarin in patients with non-valvular AF. Continuous Warfarin therapy has been advocated to avoid the need for bridging anticoagulation at the time of elective surgical procedures such as CIED insertions or revisions. Bridging can increase bleed rates and prolong hospital stay. However, clinical studies show major bleeding complications in 43.5% of such patients in the perioperative period. (3) It is proposed that Edoxaban 60 mg when administered up to 18 to 24 hours before after the CIED procedure and resumed 12 to 24 hours after the procedure could potentially reduce this bleeding risk without loss of efficacy in stroke prevention.

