At randomization, subjects will be provided with a drug kit containing either open-label Edoxaban or Warfarin for 30 days at a randomization visit. Patients randomized to Warfarin will take Warfarin on the day of procedure and patients randomized to Edoxaban will receive no drug on the day of the procedure.

Routine clinical care will be implemented with patients being scheduled for discharge within 24 hours of admission to maintain ambulatory procedural status. Patients requiring longer lengths of stay will have documentation of conditions warranting such care.

The routine standard of care (SOC) is instituted after the procedure, with a pre-discharge visit (4 to 24 hours after procedure), wound care visit (usually 1 to 2 weeks after the procedure) and standard device clinical follow-up procedures. These can include one month, three month or six month visits or remote monitoring as clinically employed in the study.

In the event of an acute procedural bleed, blood products or vitamin K may be administered. In this case, the patient will be counted as having met the primary endpoint. The primary outcome of major bleed will be assessed at the 30-day visit. The medical monitor will confirm that the primary endpoint has been assessed.

After the 30-day assessment, patients will continue to take the randomized anticoagulant unless it becomes medically necessary to change it. The MACE components will be collected at the time of the 6-month in-clinic visit.

There will be a telephone follow-up at 3 months after the CIED procedure for MACE and hospitalizations and vital status. There will be a face to face visit at 6 months which will result in study follow up completion and final patient assessment for safety endpoints, hospitalizations and vital status.

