4.2 Justification of key elements of study design

4.2.1 Primary Endpoint

Peri-procedural bleeding and major local bleeding is of clinical concern for patients who require anticoagulation. Though catastrophic bleeding is rare, bleeding requiring clinical intervention is more frequent and can be studied in a modestly sized trial. Unlike strict use of change in hemoglobin, the need for intervention with vitamin K or blood products is recognizable to patients. Reduction in the need to administer an intervention for a procedural bleed should also result in lower health care resource utilization and costs.

Major local or systemic bleeding is defined as one of the following events:

- Significant hematoma requiring further surgery, resulting in prolongation of hospitalization, or requiring interruption of oral anticoagulation therapy
- Blood transfusion (permitted if hemoglobin is below 8 gm%, or 9 gm% in patients with active myocardial ischemia e.g. acute coronary syndrome)
- Surgical or interventional procedure to control bleeding that is symptomatic (shock, severe hypotension (90 mm hg systolic) or angina or myocardial infarction, which is not amenable to conservative measures (pressure dressing, ice packs) or volume expansion with intravenous fluids)
- Use of reversal agent injection to control bleeding leading to clinically manifest shock (e.g. hypotension requiring pressors, oliguria etc.) or death, severe and symptomatic hypotension (90 mm hg systolic or lower) or angina or hemoglobin decline to below 8 gm% not amenable to conservative measures (pressure dressing, ice packs or volume expansion with intravenous fluids)
- Hemorrhage leading to stroke or eventual fatality

(INR- guidelines for vitamin K injection or blood products will be established- see guideline below).

(aPTT or anti- factor Xa assay may or may not be available for Edoxaban to guide reversal – clinical and Hemoglobin guidelines as established above will be employed to guide use of reversal with blood products or transfusion).

Recommendations for Managing Elevated INRs or Bleeding in Patients Receiving VKAs

Condition	Suggested Intervention
INR less than 4.5 but above	Hold or reduce Warfarin dose. Resume Warfarin when INR is therapeutic.

therapeutic	

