6.1.3 Follow-up Open Label Phase

[figure not shown]
Subjects randomized to continuous Warfarin should have an INR in the first month, and continue monthly INRs as per standard practice guideline recommendations. Warfarin dosage should be adjusted according to standard practice to keep patients in the therapeutic range. Subjects randomized to Edoxaban should take it once daily per package dosing instructions (Edoxaban 60 mg daily dose for

creatinine clearance 50 to 95 ml/min and Edoxaban 30 mg for creatinine clearance of 30 to 49 ml/min). Subjects will be followed for an additional five months with a phone follow up at 3 months (± 1 week) and final follow up visit at 6 months (± 1 week). After the final follow up visit or after the subject is terminated from the study, subjects on Edoxaban transitioning to Warfarin should be maintained on Edoxaban until the INR is 2.0 or higher before Edoxaban discontinuation in accordance with drug labeling.

7. Study Visits

This study consists of three parts: a run-in or eligibility phase, an acute phase and a follow-up phase. Figure 2 for shows a diagram of study activities. Table 2 and Appendix A show visits.

Figure 2: Study events

Eligibility will be assessed when subjects have completed 3 weeks of Warfarin dosing. The procedure should be scheduled 5 to 15 days after randomization so that subjects are adequately anticoagulated with Warfarin or Edoxaban. The last dose of Edoxaban will be administered less than 24 hours prior to the procedure. Randomization will be obtained via IVRS once eligibility has been confirmed and the procedure has been scheduled.

On the day of the procedure, Warfarin will be continued and Edoxaban will be interrupted. Edoxaban dosing will resume a minimum of 16 and a maximum of 24 hours following the procedure. During and after the procedure, subjects will be assessed for safety and efficacy endpoints for bleeding and

embolism respectively as well as major adverse cardiovascular events (MACE). Edoxaban subjects will in general be discharged on the same day as the procedure, whereas Warfarin subjects will have their discharge timing determined on an individual basis by the investigator.

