After discharge, subjects must return to the lab that drew the pre-procedure sample for another blood sample. This post-procedure blood draw should occur 24 to 48 hours after the procedure. The subjects will then resume the standard of care (SOC) follow-up. The SOC includes a pre-discharge visit (4 to 24 hours after procedure), wound care visit (usually 1 to 2 weeks after the procedure) and standard device clinical follow-up procedures. These can include one month, three month or six month visits or remote monitoring as clinically employed in the study.

The primary outcome assessment visit should be 30-days post procedure \pm 3 days. Assessments including focused H&P, concomitant medications, NYHA class, adverse events and hospitalizations will be collected. If a bleeding event has occurred, details including the date, time, required intervention and outcome should be recorded. Documentation of intervention may include the hospital order for vitamin K or blood products.

There will be a telephone follow-up at 3 months after the CIED procedure for MACE and hospitalizations and vital status. The final safety visit should be scheduled 6 months \pm 14-days post procedure or at the time of discontinuation if possible. Assessments including focused H&P, concomitant medications, NYHA class, adverse events and hospitalizations will be collected. If the investigator suspects that a MACE event has occurred, a MACE CRF should be completed.

Table 2: Schedule of study procedures and visits

Time point	Pre-procedure	Procedure (PM or ICD)	Post-procedure					
			Blood Draw	SOC Post Op	1	2	3	
								24-48 h
Demographics								
Medical & AF History	+							
Focused H & P					+			+
Con Meds	+				+			+
NYHA Class	+				+			+
Hemoglobin	+		+					
Procedure Details	PM or ICD							
Adverse Events	+	+		+	+	+	+	+
Hospitalizations	+				+			+

* Phone call

8. Assessment of Safety and Monitoring

Safety monitoring during the study will be performed by medical and clinical monitors and the coordinating center. Sites will be monitored by a clinical monitor at least once during this short trial. At the time of the site visit, the monitors will review implant procedure reports for all cases enrolled. Any issues or problems discovered will be discussed with the investigator; corrective action will be taken as necessary. Any findings will be documented in the monitoring reports and follow-up correspondence.

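### Discharge is planned differently by arm, and a prolonged stay alone can make a hematoma a primary event, with no reference stay tied to the endpoint and no rule for readmission

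*Combined protocol and SAP*

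**What the plan says.** The first item of the major-bleeding definition in section 4.2.1 is "Significant hematoma requiring further surgery, resulting in prolongation of hospitalization, or requiring interruption of oral anticoagulation therapy". The three consequences are alternatives, so a longer stay is enough by itself. The item gives no expected stay and says nothing about a patient who has gone home and comes back.

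Three other places bear on length of stay:

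- Section 7 (Study Visits) sets discharge by arm: "Edoxaban subjects will in general be discharged on the same day as the procedure, whereas Warfarin subjects will have their discharge timing determined" case by case by the investigator.
- Section 4.1 sets one schedule for everyone: "Routine clinical care will be implemented with patients being scheduled for discharge within 24 hours of admission to maintain ambulatory procedural status". It adds: "Patients requiring longer lengths of stay will have documentation of conditions warranting such care".
- Section 7 also describes the usual aftercare for both arms: "The SOC includes a pre-discharge visit (4 to 24 hours after procedure").

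Drug timing around the procedure differs too: "On the day of the procedure, Warfarin will be continued and Edoxaban will be interrupted". Section 7 continues: "Edoxaban dosing will resume a minimum of 16 and a maximum of 24 hours following the procedure". Section 2 gives a slightly wider window, with Edoxaban "resumed 12 to 24 hours after the procedure".

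Section 4.2.3 provides for blinded committee review of potential primary events. Section 3.3 lists hospitalization after discharge as an exploratory event only. Section 8.2 defines a serious adverse event to include one that either causes or lengthens a hospital stay.

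**The concern.** Prolongation has meaning only against a planned stay, and section 7 plans a different stay for each arm. The same hematoma, managed in the same way, could then count in one arm and not in the other because of the discharge plan rather than the bleeding. Treatment is known to the investigator who decides when a Warfarin patient goes home.

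The primary endpoint carries a non-inferiority claim with a 1.5-point margin and a handful of expected events. A component whose scoring depends on the arm could move the result toward either conclusion. Section 4.2.3 accepts that open-label designs carry more risk of bias and relies on a low-subjectivity endpoint to limit it. This limb weakens that safeguard.

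**Working it through.** **1. The plan's own figure.** Inputs from sections 10 and 10.2: Warfarin rate 0.0351, Edoxaban rate 0.005, margin 0.015, one-sided alpha 0.025, power 80%, 1:1 allocation. The event is harmful, so the distance from the margin is 0.015 + 0.0351 − 0.005 = 0.0451.

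n per arm = [0.0351 × 0.9649 + 0.005 × 0.995] × (1.960 + 0.842)² / 0.0451² = (0.03387 + 0.00498) × 7.849 / 0.002034 = 149.9, so 150 per arm and 300 in total. The plan's figure reproduces. An exact unconditional score test (an assumption, since section 10.3 says only that an exact test will be used) gives 79.6% power. This point does not challenge the sample size.

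**2. How a stay-only hematoma scores under the current text.** Take a significant hematoma with no surgery, anticoagulant interruption, transfusion, vitamin K or other reversal.

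| When it appears | Edoxaban (planned home same day) | Warfarin (investigator decides) |
|---|---|---|
| Before same-day discharge; kept overnight, home within 24 h of admission | Longer than the section 7 plan, so may score; within the section 4.1 schedule, so may not | Does not score if an overnight stay was intended anyway |
| After same-day discharge, up to about 24 h | Already home; can qualify only as a readmission, which the limb does not name | If kept overnight, still in hospital; can qualify as a prolonged stay |
| After about 24 h, to day 30 | Home; readmission only | Home under section 4.1; readmission only |

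The first row can over-count Edoxaban relative to Warfarin, and the second can under-count it. The third is a gap in the definition that both arms share. The second row covers the period around the Edoxaban restart at 16 to 24 hours, which usually falls after a same-day discharge.

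**3. How few events carry the result.** Expected events at 150 per arm are 150 × 0.0351 = 5.27 for Warfarin and 150 × 0.005 = 0.75 for Edoxaban. One event moves the risk difference by 1/150 = 0.67 points, or 0.67/1.5 = 44% of the margin. Under the exact score test, 0, 1, 2 or 3 Edoxaban events need at least 2, 4, 6 or 8 Warfarin events for non-inferiority.

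**4. Illustration under assumed error rates, 150 per arm.** False non-inferiority is evaluated with Edoxaban truly at the margin (5.01% against 3.51%), and power at the planning rates.

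| Assumption | False non-inferiority | Power |
|---|---|---|
| No misclassification | 2.3% | 79.6% |
| 10% of events missed in both arms | 2.6% | 76.8% |
| 10% missed, Edoxaban only | 3.7% | 81.5% |
| Edoxaban over-counted by 10% | 1.4% | 77.7% |
| 10% missed, Warfarin only | 1.6% | 74.7% |

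The test searches the Warfarin rate up to 30%. With the full range searched, the false non-inferiority column reads 2.0%, 2.4%, 3.3%, 1.2% and 1.4%. At 200 per arm it is 2.2%, 2.6%, 3.9%, 1.3% and 1.5%.

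Steps 3 and 4 describe the test's sensitivity to any misclassified event. They do not measure this defect, because the documents do not give the share of events that qualify on stay alone.

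**The case against.** The strongest reply is that the protocol already contains the needed controls. The limb is causal: the hematoma must be what lengthened the stay, so a longer default Warfarin stay does not score. Section 4.1 gives both arms the same 24-hour schedule and asks for the reasons for longer stays. Section 7 can be read as arm-specific practice under that ceiling, since it does not say that Warfarin patients stay beyond 24 hours. A blinded committee reviews each potential event. The 30-day visit collects hospitalizations and bleeding details, so a readmission would be on file. The affected group may be very small, because holding the anticoagulant already qualifies a hematoma and the section 4.2.1 guidance is to hold Warfarin for serious bleeding.

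Most of this stands, and it limits the point. The arm-specific part of the readmission gap is confined to roughly the first 24 hours. The assumed error rates in the illustration apply to all events in an arm, and its boundary case sets Edoxaban at ten times its planned rate; at the planned rate, 10% of Edoxaban events is 0.075 of an event.

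It does not remove the point. Causation still has to be judged against an intended stay, and section 7 states a different intention for each arm. The section 4.1 schedule is not linked to the endpoint. The committee can apply only the definition as written, and that definition does not say whether a readmission counts.

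**Conclusion.** The concern holds in limited form and should be fixed. A stated arm-specific discharge plan feeds a component of an open-label primary endpoint that has neither a linked reference stay nor a readmission rule. Its size cannot be derived from the documents and is probably small; the reason to act is that few events are expected and the correction is cheap.

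A reader might infer three stronger things that the documents do not support:

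- **That the plan biases the trial toward Edoxaban.** The direction is open, because the same text can over-count or under-count Edoxaban.
- **That the protocol has no reference stay at all.** Section 4.1 supplies a partial one.
- **That the type I error is inflated to a particular value.** The figures above rest on assumed error rates, and equal loss in both arms leaves the error close to nominal.

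The conclusion assumes that some hematomas qualify on stay alone and that the section 7 discharge sentence is followed in practice.

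**What to change.** 1. Delete the arm-specific discharge sentence in section 7 and apply the section 4.1 schedule, discharge within 24 hours of admission, to both arms.
2. Reword the stay limb identically for both arms and on that same clock: a significant hematoma that is the documented reason for a stay beyond the scheduled 24 hours from admission, or that requires readmission within 30 days. This agrees with the serious adverse event definition in section 8.2. Leave the surgery and anticoagulant-interruption limbs unchanged.
3. Record admission and discharge times on the CRF; the visit schedules list hospitalizations but no such times.
4. Report a sensitivity analysis of the primary endpoint without stay-only events.

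Cost: protocol wording and two CRF fields. An overnight stay that ends within 24 hours would no longer count, in either arm, while readmissions would count, so event counts may shift slightly from the 3.51% planning rate. The match to that rate cannot be checked, because the source trial's hematoma definition is not reproduced. As a guide, power at 150 per arm goes from 79.6% to 75.8% if only the Edoxaban rate rises to 0.6%, or to 84.1% if both rates rise by a fifth (0.6% and 4.21%). Without stay-only events, power would be 76.8% or 73.5% if these are 10% or 20% of events in both arms, so that analysis should remain supportive.

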4.2.2 Choice of continuous Warfarin as a comparator

Heparin bridging was standard of care until the BRUISE-CONTROL study showed a reduction of bleeds with continuous Warfarin compared to heparin combined with bridging therapy. No robust studies of other anticoagulants in procedural settings have been performed to date, so continuous Warfarin is the only suitable comparator.

4.2.3 Timing of primary endpoint evaluation

Other studies in cardiovascular medicine such as those for interventions during acute myocardial infarction or chronic ischemic heart disease consider bleeding events through 30-days post-procedure, and so it is a commonly used clinical timeframe. Because this trial is examining a surgical intervention, there is potential for bleeds and other acute complications. If this happens, the open label design allows investigators to make appropriate treatment decisions as quickly as possible. As always, open-label designs have an increased risk of bias. To combat this risk, we have defined a primary endpoint with minimal patientivity (see section 4.2.1). We will also have a blinded adjudication committee review each potential primary endpoint event to confirm that the study definition has been met.

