DURATION OF PATIENT PARTICIPATION AND DURATION OF STUDY	
Screening: 7-26 days
 
Treatment: 5 days of randomized therapy prior to procedure (which is a single day)
 
Follow-up: 180 days

CONCOMITANT MEDICATIONS	Allowed as per approved FDA guidelines
EFFICACY EVALUATIONS	
PRIMARY ENDPOINT	Major local or systemic bleeding as defined in the protocol at 30 days after implant procedure
SECONDARY ENDPOINTS	The secondary objectives are to compare the rates of thrombotic events (embolism or stroke) through 6 months following the procedure in the Edoxaban and Warfarin groups and the rates of MACE events through 6 months following the procedure in the Edoxaban and Warfarin groups
OTHER EVALUATIONS	The exploratory objectives are to compare rates of hemoglobin reductions from pre-procedure to 24-48 hours post procedure in the Edoxaban and Warfarin groups
SAFETY EVALUATIONS	Safety monitoring during the study will be performed by an independent data monitoring committee (DMC), as well as medical and clinical monitors

	and the coordinating center. Sites will be monitored by a clinical monitor at least once during this short trial. Clinical sites will be required to report all procedure related complications, deaths and major adverse events to the medical monitor within 24 hours of learning of the event. All events will be adjudicated by an independent events committee.
PLANNED INTERIM ANALYSES	When approximately 200 subjects have completed the study through the 30-day visit, an interim analysis for safety will be conducted by an independent data monitoring committee. Serious adverse events will be monitored by the committee on an ongoing basis throughout the study. Based on the primary outcome in these 200 subjects, the study may continue to enroll up to 200 additional subjects, or be terminated.
STATISTICS Primary Analysis Plan	This study contains an internal pilot, and the primary endpoint will be evaluated when 200 patients have reached 30-days post procedure or withdrawn. Based on the primary outcome in these 200 patients, the study may enroll up to 200 additional subjects, or be terminated. Bleeding rates will be compared for non-inferiority using a 1-sided exact test (Primary Endpoint). If non-inferiority of Edoxaban is demonstrated, superiority will be assessed using a 2-sided exact test (Secondary Endpoint).

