4.1 Overview

This study is a randomized, open label, active-controlled trial with a safety extension (follow-up phase). It is designed to compare bleeding, local or systemic, within 30 days of cardiac rhythm device implant (acute phase) for non-valvular AF among patients randomized to continuous Warfarin or interrupted

Edoxaban. Randomization will be stratified by device type and HAS-BLED score (≤ 2 or ≥ 3). Patients will be randomized in a 1:1 ratio to receive interrupted Edoxaban or continuous Warfarin. This study contains an internal pilot opportunity to adjust the sample size or terminate the study, and there will be an interim analysis of the primary endpoint when 200 patients have reached 30-days post procedure or withdrawn. Based on the primary outcome in these 200 patients, the study may:

[figure not shown]
- Enroll 200 additional patients (pacemaker capped at 100 patients, ICD capped at 150 patients)
- Enroll 100 additional patients
- Be terminated

The study design is outlined in Figure 1.

Figure 1:

Study Design Flow Chart

Study Timeline

- Seamless design, enrollment does not stop between phases
-  Opportunity to stop if Part I objectives are not met
- Minimal resource commitment to Part II if Part I objectives not met
- For Part II, all sites enrolling, experience should lead to improved data quality compared to Part I
- Phases analyzed separately (primary) and combined

Eligible subjects must be stable on a therapeutic dose of Warfarin (INR 2-3) for three weeks prior to randomization. If potential patients are taking an anticoagulant besides Warfarin, or otherwise not meeting this criteria, must be switched to Warfarin and complete 3 weeks of dosing with INRs in the therapeutic range (run-in period) at randomization.

Comment [s1]: Segment into two sentences.
Insert period

Comment [s2]: delete

Comment [s3]: delete

Comment [s4]: Insert

The final INR should be performed on the day of randomization, and the procedure should be scheduled a minimum of 5 days and at most 15 days after randomization. Once eligibility has been confirmed and informed consent has been obtained, patients will be randomized via an interactive secure web randomization system. Patients will be randomized in a 1:1 ratio to Edoxaban or Warfarin. Randomization will be blocked by HAS-BLED score, and based on a randomization list, which will be created prior to commencement of the study.

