9.2 Site training and monitoring

Prior to study initiation, all investigators and research coordinators will be trained in the study protocol at a central investigators meeting. Each clinical site will be visited by trained clinical monitors at least once during the study to make sure that study protocol procedures are being followed, consent is being

obtained per regulation and data are being collected contemporaneously and accurately. Clinical monitoring visits will be scheduled as needed thereafter. Any serious complications of the implant procedure will be reviewed by the DMC and a summary of the failures and complications will be presented to the DMC at each meeting.

10. Assessment of Non-Inferiority Hypothesis and Data Analysis

This study was designed based on a non-inferiority hypothesis, with an overall type I error rate of 0.025 (1-sided). The non-inferiority margin is 1.5%.

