10.2 Sample size calculation (Appendix B)

It is possible, due to the low event rate in the Edoxaban arm and small sample size, that we could see no events in this arm. Thus, these sample size calculations are based on absolute risk differences rather than relative risk differences. Assuming event rates for Warfarin and Edoxaban of 3.51% and 0.5%, respectively, 300 total patients provides approximately 80% power to detect non-inferiority (margin 1.5%).

This study is a randomized, open label, active-controlled trial with an open-label safety extension, designed to compare local or systemic bleeding within 30 days of cardiac rhythm device implant for non-valvular AF among patients randomized to continuous Warfarin or interrupted Edoxaban. The DMC will review a formal interim analysis of the first 200 patients. Based on this analysis the DMC will make a recommendation about whether the study should be stopped or continued as planned. They may recommend that the study:

1. Be terminated for futility
2. Enroll an additional 100 patients in part II
3. Enroll an additional 200 patients in part II

Details about the criteria for this decision will be included in an interim statistical analysis plan and/or the DMC charter prior to the first data safety review. Because there is no opportunity to stop for efficacy after the first 200 patients, no type I error adjustment for the final analysis is necessary.

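### Blinded adjudication confirms referred bleeds but, as described, cannot recover unreferred ones, and ascertainment could differ by arm in either direction

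*Combined protocol and SAP*

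**What the plan says.** The trial is open label. Section 4.2.3 names the bias risk and offers two protections: an endpoint meant to need little judgement, and blinded review. On the second it says: "We will also have a blinded adjudication committee review each potential primary endpoint event to confirm that the study definition has been met". The safety row of the synopsis is broader: "All events will be adjudicated by an independent events committee".

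The described sources of events are the sites. Section 8 has them report procedure-related complications, deaths and major adverse events to the medical monitor within 24 hours. At the 30-day visit, Section 7 says: "If a bleeding event has occurred, details including the date, time, required intervention and outcome should be recorded". The only stated review of every enrolled case is the monitors' reading of implant procedure reports (Section 8). Under Section 4.1 the medical monitor confirms that the endpoint was assessed.

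On discharge, Section 7 says "Edoxaban subjects will in general be discharged on the same day as the procedure" and leaves Warfarin discharge to the investigator, case by case. Section 4.1 instead schedules all patients for discharge within 24 hours of admission. The first endpoint component in Section 4.2.1 is a significant hematoma that needs further surgery, prolongs the hospital stay or interrupts oral anticoagulation.

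**The concern.** A committee that confirms or rejects what it receives works in one direction only: it lowers the count. If a bleed is not recognised or not referred, blinded review leaves the error in place. The endpoint components most open to this are a prolonged stay and an interruption of anticoagulation. Both are decisions by clinicians who know the arm, and the first depends on a discharge plan that Section 7 sets by arm.

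The 24-48 hour hemoglobin is drawn in both arms and would be a natural neutral screen, but nothing in the plan makes a fall trigger review.

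Events are few. In a non-inferiority trial on an absolute margin, losing one or two events in the test arm moves the result toward success. Losing them in the control arm moves it the other way.

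**Working it through.** **Inputs from the documents.** Warfarin 3.51%, Edoxaban 0.5%, 300 patients, about 80% power (Section 10.2); one-sided type I error 0.025 (Section 10); "The non-inferiority margin is 1.5" percentage points (Section 10); 1:1 allocation (Section 4.1); maximum 400 patients (synopsis).

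**Assumptions.** Section 10.3 does not name its exact test; I used an exact unconditional test ordered by the Farrington-Manning score. The share of bleeds missed is not in the documents and is shown as a range.

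**1. The plan's own figure.** With unpooled variance, and a bleed counted as a harm:

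n per arm = (1.960 + 0.842)² × [0.0351 × 0.9649 + 0.005 × 0.995] / (0.015 + 0.0351 − 0.005)²
= 7.849 × 0.03884 / 0.0451² ≈ 149.9, so 150 per arm and 300 in total.

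Power at 150 per arm is 80.0% by the normal approximation and 79.6% by the exact test. The stated design reproduces.

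**2. Expected events at 150 per arm.**
- Planning rates: 150 × 0.0351 = 5.3 Warfarin and 150 × 0.005 = 0.75 Edoxaban, about 6 in all.
- At the margin (Edoxaban 3.51% + 1.5% = 5.01%): 5.3 Warfarin and 7.5 Edoxaban, about 12.8 in all. The error rates below apply here.

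**3. Edoxaban bleeds missed, Warfarin fully captured.** Observed Edoxaban rate = 5.01% × (1 − share missed). Probability of declaring non-inferiority when Edoxaban is truly 1.5 points worse:

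| Edoxaban bleeds missed | Observed Edoxaban rate | 150 per arm | 200 per arm |
|---|---|---|---|
| 0% | 5.01% | 2.3% | 2.3% |
| 10% | 4.51% | 3.7% | 3.9% |
| 20% | 4.01% | 5.9% | 6.6% |
| 30% | 3.51% | 9.2% | 11.0% |

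The whole 1.5-point excess disappears when 1 − 3.51/5.01 = 29.9% are missed, which is about 2 of 7.5 events. The asymptotic score test gives nearly the same values at 150 per arm (2.4, 3.8, 6.0 and 9.3%).

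**4. Warfarin bleeds missed, Edoxaban fully captured.** Missing 20% makes the observed Warfarin rate 3.51% × 0.8 = 2.81%. The error falls to 1.1% at 150 per arm and 0.9% at 200.

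**5. The same share missed in both arms.** Missing 20% in each gives 3.0% at 150 per arm and 3.1% at 200. Because the margin is absolute, equal under-capture is not fully harmless either.

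**The case against.** The strongest reply is that ascertainment is broader and more even than the concern suggests.

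- **Shared contacts.** Both arms have the pre-discharge visit, the 24-48 hour blood draw, the wound visit and the 30-day visit, and the visit tables are not split by arm. This stands. The stated differences are discharge timing and INR checks for Warfarin subjects (Section 6.1.3).
- **Broad reporting.** A site need not call something an endpoint to report it. All adverse events go on the CRF (Section 8.1), an event that requires or prolongs hospitalization is serious (Section 8.2), and Section 4.1 counts an acute procedural bleed given blood products or vitamin K as an endpoint. Transfusion, re-operation, stroke and death leave hospital records. This narrows the exposure, but every one of these reports still starts at an unblinded site, and no rule turns a report into a referral.
- **Silence is not exclusion.** A committee charter outside these documents could add another route. A reader might infer that the committee sees only what sites choose to flag. The documents do not say so; they only describe no other route.
- **Direction.** A reader might also infer that Edoxaban bleeds are the ones that would be missed. The documents do not support that. Against a planned same-day discharge an Edoxaban overstay is easy to see, while a Warfarin stay has no fixed reference. On the other side, the planned Edoxaban interruption could hide one caused by bleeding.
- **Adjudication scope.** The synopsis and Section 4.2.3 need not contradict each other, since all events can include potential primary events. What remains is that the scope should be worded once.

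**Conclusion.** The point holds as a gap in the plan's stated defence against open-label bias. Blinded confirmation, as described, cannot correct differential referral. The arm-specific discharge text gives a concrete reason why referral could differ, and a measurement already taken in everyone is not used to close the gap.

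It does not hold as a finding that the trial is biased toward non-inferiority. Direction and miss rate are both assumptions. If 10 to 30% of Edoxaban bleeds went unreferred and Warfarin capture were complete, the nominal 2.5% error would be 3.7 to 9.2% at 300 patients and 3.9 to 11.0% at 400. With 20% of Warfarin bleeds missed instead, it would be 1.1% at 300 patients. These figures also rest on Edoxaban being truly at the margin, a Warfarin rate of 3.51%, and the score-ordered exact test. The change is cheap and should be made.

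**What to change.** In Section 4.2.3 and the committee charter, prespecify triggers applied identically in both arms. Any one of them sends a case, masked to arm, to the existing committee whatever the site's opinion:

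- transfusion;
- reversal agent;
- pocket re-operation;
- any hematoma or bleeding adverse event;
- prolonged or repeat hospitalization;
- anticoagulant interruption beyond the protocol-planned one and attributed to bleeding (without this limit the trigger would fire for every Edoxaban patient by design);
- a 24-48 hour hemoglobin fall at one named threshold.

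For the last trigger, first reconcile the two values in Section 3.3. A fall of 2 g/L is 0.2 g/dL, and 1.5 Gm% is 1.5 g/dL, so they differ by a factor of 7.5 and the choice drives the number of dossiers.

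Also:

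- Add yes/no eCRF items for transfusion and reversal agent at the 30-day visit. Neither is in the visit tables, and Section 9.1 collects concomitant medication by class for common cardiovascular drugs.
- Define prolongation of hospitalization, for endpoint purposes, against a reference common to both arms.
- Word the adjudication scope the same way in the synopsis and Section 4.2.3.
- Reconcile the discharge statements in Sections 4.1 and 7. Which of them should apply is for the sponsor and investigators to decide.

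The cost is edit checks, a few eCRF fields, charter wording and some additional dossiers for the existing committee. No new visits or procedures are needed.
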